## 6.3 Patient numbering, treatment assignment, randomization

### 6.3.1 Patient numbering

Each patient is identified in the study by a Patient Number (Patient No.) that is assigned when the patient is first enrolled for screening and is retained as the primary identifier for the patient throughout his/her entire participation in the trial. The Patient No. consists of the Center Number (4 digit number for Center No. as assigned by Novartis to the investigative site) with a sequential patient number suffixed to it (3 digit number for Patient No.), so that each patient is numbered uniquely across the entire database. Upon signing the informed consent form (ICF),

the patient is assigned to the next sequential Patient No. available in the electronic data capture (EDC) system.

Patients who have been screen failures but are rescreened (see [Section 8.1](#)) will be assigned a new Patient No.

### **6.3.2 Treatment assignment, randomization**

No randomization will be performed in this study. The assignment of patients to treatment will be coordinated by Novartis.

## **6.4 Treatment masking**

Treatment will be open to patients, investigator staff, persons performing the assessments, the Clinical Trial Team, and the Central Reading Center (CRC).

## **6.5 Dose escalation and dose modification**

In this study, brolocizumab 6 mg (0.05 mL) will be administered by IVT injection every 4 weeks (monthly) for the first 3 doses. Thereafter, brolocizumab is administered every 12 weeks (3 months). The investigator can individualize treatment intervals based on disease activity as assessed by visual acuity and/or anatomical parameters so that the treatment interval can be as frequent as every 8 weeks (2 months). Patients needing the q8w treatment regimen will remain on this regimen until the end of the treatment at Week 40/Week 44.

No study treatment dose modification is allowed and no deviation to the allowed dose intervals (in accordance with disease activity assessments) is allowed.

Interruption of study treatment is allowed if warranted by an AE or cataract surgery ([Section 6.2.1.1](#)).

### **6.5.1 Follow-up for toxicities**

Not applicable.

## **6.6 Additional treatment guidance**

### **6.6.1 Treatment compliance**

The date and time of all study treatment injections administered during the study and any deviations from the protocol treatment schedule will be captured by the study personnel or by the field monitor on the appropriate study treatment dispensing form.

Exposure to the study treatment will be based on the number of injections administered. Compliance with the study treatment will be assessed by the field monitor at each visit using PFS counts and information provided by the pharmacist or study personnel.

### **6.6.2 Emergency breaking of assigned treatment code**

Not applicable as this is a single-arm, open-label study.

## **6.7 Preparation and dispensing of study treatment**

Each study site will be supplied with study drug in packaging as described under the investigational drugs section ([Section 6.1.1](#)).

A unique medication number is printed on the study medication label. The study medication has a 2-part label (base plus tear-off label); immediately before dispensing the package to the patient, site personnel will detach the outer part of the label from the package and affix it to the patient's source document. The number must be written into the eCRF.

### **6.7.1 Handling of study treatment**

Study treatment must be received by a designated person at the study site, handled and stored safely and properly and kept in a secure location to which only the investigator and designated site personnel have access. Upon receipt, all study treatment must be stored according to the instructions specified on the labels and in the Investigator's Brochure (IB). Clinical supplies are to be dispensed only in accordance with the protocol. Technical complaints are to be reported to the respective Novartis CO Quality Assurance.

Medication labels will be in the local language and comply with the legal requirements. They will include storage conditions for the study treatment but no information about the patient except for the medication number.

[figure not shown]
The investigator must maintain an accurate record of the shipment and dispensing of study treatment in a drug accountability log. Monitoring of drug accountability will be performed by monitors during site visits or remotely and at the completion of the trial.

At the conclusion of the study, and as appropriate during the course of the study, the investigator will return all unused study treatment, packaging, drug labels, and a copy of the completed drug accountability log to the Novartis monitor or to the Novartis address provided in the investigator folder at each site.

### **6.7.2 Instruction for prescribing and taking study treatment**

There will be 2 treatment phases (see [Figure 6-1](#)).

#### **Figure 6-1 Treatment regimen**

\* The end of treatment will occur at either Week 40 or Week 44 according to the treatment schedule.  
DA=disease activity, IVT=intravitreal, Q8=every 8 weeks, Q12=every 12 weeks, W=week, OCT= optical coherence tomography

### Initiation phase

In the initiation phase, treatment with brolocizumab 6 mg will initially be injected 3 times at 4-week intervals, at Screening/Baseline/Day 1, Week 4 and Week 8. Following the loading doses, each patient will be injected q12w or q8w up to Week 40 or Week 44 (according the treatment regimen).

During the initiation phase, disease activity will be assessed at Day 1, Week 4 and Week 8.

### q12w/q8w treatment phase

The mandatory visit at Week 12 will be performed to evaluate the primary endpoint of the study. No treatment will be administered at Week 12; the next visit will take place at Week 16. Disease activity will be assessed at Week 12 for endpoint assessment purposes.

The q12w/q8w treatment phase starts at Week 16 and is defined as follows:

- Following Week 8, treatment intervals will be either 8 weeks or 12 weeks. A patient must be discontinued from further study treatment if treatment is required more frequently, i.e., every 4 weeks.
- The first assessment of disease activity during this phase will be performed at the Week 16 visit by the investigator.
- Based on investigator's judgment of visual and/or anatomic outcomes, the treatment can be adjusted by the investigator to a q8w treatment regimen if there is disease activity as

provided in the guidance to the investigators, e.g. decrease of visual acuity and/or other signs of the disease (e.g. IRF, SRF, sub-RPE fluid, retinal hemorrhage, CRT increase, etc.).

- The disease activity assessment is performed at each subsequent visit by the investigator.
- If disease activity is identified, the patient will be reassigned to receive injections q8w thereafter up to Week 40/Week 44.
- Regardless of treatment administration, Week 16 and Week 48 visits are mandatory.
- The timing of the interim visits between Week 16 and Week 48 will depend on the patient's injection regimen, i.e. q12w or q8w.
- No visits are planned between the injection visits.
- The last potential study treatment may be administered at the Week 40 visit or at the Week 44 visit according to the patient's treatment regimen.
- A disease activity assessment will also be performed at the Week 48/EOS visit; however, no study treatment will be administered.

The different types of visits occurring through the study are summarized in [Table 6-3](#) with a description of when disease activity assessment and treatment take place.

**Table 6-3 Disease activity assessment and treatment occurrence according to visit type**

Type	Study Period or Phase	Disease Activity Assessment	Treatment
Screening / Baseline (Day 1) visit	Initiation phase	Yes	Yes
Week 4 visit	Initiation phase	Yes	Yes
Week 8 visit	Initiation phase	Yes	Yes
Week 12 visit	Primary endpoint	Yes	No
Week 16 visit	Q12w / q8w phase	Yes	Yes, according to disease activity assessment
Treatment visits (interim visits between Week 20 and Week 48 where treatment is administered)	Q12w / q8w phase	Yes	Yes
ETD visit and EOS visit (Week 48)	Follow-up	Yes	No

Brolucizumab should be administered in the study eye on the day of the study visit or, if this is not possible, within 3 days after the occurrence of the study visit or no later than within the visit window ( $\pm 7$  days) as described in [Section 3](#) and [Section 8](#). When assessments and treatments take place on the same day, treatment must occur after completion of the efficacy assessments described in [Section 8.3](#) and pre-injection safety measures (tonometry, slit lamp and fundus examinations) described in [Section 8.4.3](#). If study visit assessments and the corresponding treatment occur on separate days, a repeat safety check-up should be performed prior to treatment of the eye and results documented in the source documents. If any safety concern arises related to the study eye that, in the opinion of the investigator, may be further impacted by the study treatment or injection procedure, treatment needs to be cancelled. Injections are contraindicated in patients with active intraocular or periocular infections and in patients with

active IOI; therefore, the investigators must verify that these conditions are not present in the study eye prior to every injection. Any AEs must be recorded in the eCRF.

If any signs of IOI are present, then an IVT injection **must not** be performed. Additional ophthalmic examination and imaging should be performed to evaluate IOI (see [Section 8.4.3](#)).

If intraocular inflammation, including retinal vasculitis, and/or retinal vascular occlusion, is confirmed, subjects should be discontinued from study treatment.

The injection procedure for brolocizumab including aseptic and antimicrobial requirements, will be performed according to local clinical practice. Injections will be administered by the investigator.

Every effort should be made to ensure that the patient adheres to the visit/treatment schedule.

### **Disease activity criteria**

Disease activity criteria will be assessed by the investigator based on whether nAMD is still active or has been re-activated. Guidance for the investigator are as follows (disease is active if at least one of the following criteria is observed by the investigator):

- BCVA decrease  $\geq 5$  letters from the best value since Baseline due to disease activity.
- Any significant increase in CRT (based on investigator assessment).
- Retinal hemorrhage.
- Intraretinal fluid or SRF due to disease activity (degenerative cysts allowed).
- Increase of sub-RPE fluid.

These criteria are for guidance only, the investigator may define disease activity based on his/her own assessment.

Anatomic parameters measured by OCT-A and by SD-OCT will be analyzed by a CRC. The main aim of the CRC analysis is to confirm anatomic features from OCT-A and SD-OCT images for the primary endpoint. The CRC will have no involvement in assessment of disease activity, which is solely the investigator's responsibility.

A patient who misses Week 16 will undergo the disease activity assessment at Week 20 as he/she would have done if the visit had not been missed. If, however, a patient misses any of the following disease activity assessment visits (Week 20, Week 32) then the patient will be assumed to have met the disease activity criterion at the missed visit and will be reassigned to an q8w regimen up to study exit.

If a patient misses Week 12, then the Week 8 values will be applied as the reference for disease activity assessments up to and including Week 44.

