## 8 Visit schedule and assessments

The Assessment Schedule for the study eye ([Table 8-1](#)) lists all of the assessments when they are performed. All data obtained from these assessments must be supported in the patient's source documentation. All data requested by eCRF must be entered in a timely manner (see [Section 11.1](#)).

A planned study visit schedule will be established at Screening/Baseline/Day 1 for all patients. All post-Baseline and/or subsequent scheduled visits will be calculated based on the Screening/Baseline/Day 1 visit date. During the q12w/q8w phase, from Week 16 to Week 44, the treatment visit intervals will be determined by the investigator, based on the patient's disease activity (see [Section 6.7.2](#)). All efforts should be made to adhere to all scheduled visits and assessments as outlined in the assessment schedule ([Table 8-1](#)).

A  $\pm 7$ -day visit window is allowed should the patient be unable to return per the scheduled visit. All efforts should be made to revert back to the planned visit schedule taking into consideration the restrictions on the minimum treatment interval for the study medication (brolocizumab).

Assessments can be performed on 2 consecutive days in which both days must occur within the  $\pm 7$  days visit window.

Treatment is intended to be administered on the day of the study visit, or if this is not possible, within 3 days after the study visit at which the per-protocol assessments took place. If study visit assessments and the corresponding treatment occur on separate days, a repeat safety check-up should be performed prior to treatment of the eye and results documented in the source documents. For all visits, efficacy assessments ([Section 8.3](#)) and safety assessments ([Section 8.4](#)) should be performed prior to any administration of study treatment.

Missed or rescheduled visits should not lead to automatic discontinuation.

If the COVID-19 pandemic limits or prevents on-site study visits, study treatment should not be administered and other study assessments may not be performed. Alternative methods of safety monitoring may be implemented. Depending on local regulations, site capabilities and patients' visit status in the study, phone calls or virtual contacts (e.g. teleconsult) can be performed for safety follow-up for the duration of the pandemic, until it is safe for the participant to visit the site again.

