## Unscheduled visits

If a patient returns to the site prior to his/her next scheduled study visit, the investigator will capture the unscheduled visit in the eCRF only in the case of a clinically significant abnormal finding.

If this finding leads to an AE and/or the decision to treat the patient prior to his/her next scheduled treatment, all the procedures listed for the Interim Visit need to be conducted and captured in the eCRF.

In the case of a treatment decision for nAMD treatment is made during the unscheduled visit (at the exception of AE treatment), the assigned study medication can not be administrated. In case of administration of an anti-VEGF medication during an unscheduled visit, it will be considered as the use of a prohibited treatment and should be managed as described in [Section 9.1.1](#).

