- Any significant increase in CRT (based on investigator assessment).
- Retinal hemorrhage.
- Intraretinal fluid or SRF due to disease activity (degenerative cysts allowed).
- Increase of sub-RPE fluid.

These criteria are for guidance only, the investigator may define disease activity based on his/her own assessment.

A patient who misses Week 16 will undergo the disease activity assessment at Week 20 as he/she would have done if the visit had not been missed. If, however, a patient misses any of the following disease activity assessment visits (Week 20, Week 32) then the patient will be assumed to have met the disease activity criterion at the missed visit and will be reassigned to a q8w regimen up to study exit.

If a patient misses Week 12, then the Week 8 values will be applied as the reference for disease activity assessments up to and including Week 44.

Fluorescein angiography: Fluorescein angiography (FA) is a diagnostic procedure that uses a special camera to record the blood flow in the RETINA – the light sensitive tissue at the back of the eye.

Color fundus photography (CFP): CFP is a diagnostic procedure that involves the use of a device known as a fundus camera to record colored images of the interior surface of the eye. The goal of this procedure is to monitor the presence of disorders and their change with time.

Fundus autofluorescence (FAF): Fundus autofluorescence imaging is an *in vivo* imaging method for metabolic mapping of naturally or pathologically occurring fluorophores of the ocular fundus.

Indocyanine green angiography (ICG): ICG is a diagnostic procedure that uses ICG dye to examine the blood flow in the choroid – the layer of blood vessels that lies underneath the retina. ICG is injected into a vein in the arm/hand. As the dye passes through the blood vessels of the eye, photographs are taken to record the blood flow.

Intraocular pressure (IOP): IOP is the fluid pressure of the eye. IOP is measured in millimeters of mercury (mmHg). Normal eye pressure is usually considered to be between 10 and 25 millimeters of mercury (mmHg).

Fundus examination: Fundus examination used to assess diagnose vitro-retinal diseases (such as retinal haemorrhage, vitreal haemorrhage, retinal tear and detachment), optic nerve defects and hereditary diseases.

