2.6.1.5 Dosing regimen of brolucizumab

The binomial proportion and 95% CI using the Clopper-Pearson method will be provided for patients who are maintained on an exclusive q12w interval following the loading phase through Week 48.

The number and percentage of q8w dose frequency patients will be presented along with 95% CI using the Clopper-Pearson method.

Duration of dose is defined as (date of last dose – start date of dose).

The summary statistics (n, mean, std, first quartile, median, third quartile, min and max) for duration of dose will be provided for patients who are maintained on an exclusive q12w interval following the loading phase through Week 48. In the study design the 3×4 -week dosing frequency, in initiation phase.

The above analysis will be done only on the study eye. The analysis will be performed on the FAS.

2.6.1.5.1 Predictive value of the first q12w cycle for maintenance of q12w treatment with brolucizumab

The probability of the first q12w interval will be derived from KM time to event analyses. KM plot will be provided. Detailed KM results will be presented including time (week), number of patients under risk at visit, number of patients with first q12w or discontinue at visit, probability of maintaining on q12w (survival probability) and 95% CI for maintaining on q12w.

Variable	Definition	
Start date	First date when patients on q12w interval	
Event	Fail maintain to q12w interval	
End date	Last date of initial q12w interval (before or on first start of q8w interval)	
Censoring (end date)	Completed/Discontinue with q12w	
Duration of time	(End date – start date) +1	

The above analysis will be done only on the study eye. The analysis will be performed on FAS.

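### A missed Week 20 or Week 32 visit counts as loss of q12w with no retinal finding behind it, so the secondary q12w results partly reflect attendance

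*Protocol*

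**What the plan says.** **The missed-visit rule.** Protocol Section 6.7.2 (Disease activity criteria) covers three cases. A patient who misses Week 16 is simply assessed at Week 20. For a patient who misses Week 20 or Week 32, "the patient will be assumed to have met the disease activity criterion at the missed visit" and q8w follows. Week 44 is not mentioned, although Protocol Section 3 lists it with Weeks 20 and 32 as a q12w assessment visit. SAP 2.1.1 (Addendum 1.0) carries the same rule, in these words: "will be assumed to have met the disease activity criterion at the missed visit and will be reassigned to a q8w regimen up to study".

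**The endpoints.** SAP 2.6.1.5 gives a Clopper-Pearson proportion for "patients who are maintained on an exclusive q12w interval following the loading phase through Week 48". In SAP 2.6.1.5.1 the Kaplan-Meier event is failure to maintain q12w, and patients who complete or discontinue while still on q12w are censored. Both use the FAS. Neither section separates a presumed switch from an observed one.

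**The dosing rules around a missed visit.**
- Protocol 6.7.2 gives maintenance intervals of 8 or 12 weeks, plans no visits between injection visits, and ties each injection to its visit and the ±7-day window.
- Protocol 6.5 says that "no deviation to the allowed dose intervals (in accordance with disease activity assessments) is allowed". It permits interruption only for an adverse event or cataract surgery.
- Under Unscheduled visits, when a decision to treat nAMD is made, "the assigned study medication can not be administrated".
- Section 8 says that a missed or rescheduled visit should not automatically end treatment. If COVID-19 prevents site visits, "study treatment should not be administered and other study assessments may not be performed". The missed-visit rule has no exemption for this.

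**The concern.** The q12w objectives ask how many patients can be held on q12w, and how well the first q12w cycle predicts that. Both are questions about the retina. A switch triggered by absence carries no information about the retina, yet the outputs record it as if it did. At Week 44 absence has the opposite effect, because no switch is presumed. A reader of the q12w results could not tell how much of the loss came from disease activity and how much from non-attendance.

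The same rule raises a second question. It presumes activity and shortens the interval, but the surrounding sections do not say when that patient is next seen and injected.

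**Working it through.** **1. How each case is scored** (Protocol 3 and 6.7.2; SAP 2.1.1, 2.6.1.5 and 2.6.1.5.1)

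| Case, patient on q12w | Regimen afterwards | Kaplan-Meier | Proportion |
|---|---|---|---|
| Attends Week 20 or 32, activity seen | q8w | event | not maintained |
| Misses Week 20 or 32, no examination | q8w by presumption | event | not maintained |
| Attends Week 44, activity seen | q8w selected | event | not maintained |
| Misses Week 44, completes the study | still q12w | censored | maintained |

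Rows 1 and 2 are indistinguishable in the outputs. Row 3 is a reading of Protocol 3 with SAP 2.1.1: no study injection follows Week 44, so the q8w choice has no later dose to act on. If the SAP is programmed so that row 3 is not an event, a missed Week 44 does not raise the estimate.

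**2. Size, by assumption.** The documents give neither a missed-visit rate nor an expected q12w proportion. Let *p* be the proportion who would stay on q12w on retinal findings, and *m* the chance of missing each of Weeks 20 and 32, independent of retinal status. Such a patient is still counted only if both visits are attended:

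reported proportion = p × (1 − m)²

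| m | p = 0.55 | Fall, points | Patients of 210 |
|---|---|---|---|
| 2% | 0.55 × 0.9604 = 52.8% | 2.2 | 5 |
| 5% | 0.55 × 0.9025 = 49.6% | 5.4 | 11 |
| 10% | 0.55 × 0.81 = 44.6% | 10.5 | 22 |

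Over p = 0.50 to 0.70 and m = 2% to 10%, the fall is 2 to 13 points. For scale, 126 of 210 (60%) has a Clopper-Pearson 95% interval of 53.0% to 66.7%. A 2-point shift is small against that; a 10-point shift is not. The formula covers only the downward effect of Weeks 20 and 32.

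**3. Dosing calendar.** The plan's own dates first. Loading injections are "at Screening/Baseline/Day 1, Week 4 and Week 8". On q12w, 8 + 12 = 20, then 32 and 44, as Protocol 3 states. On q8w from Week 8: 16, 24, 32, 40. After a switch at an attended Week 20: 28, 36, 44. After a switch at an attended Week 32: 40. All end at Week 40 or 44, as stated.

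After a missed visit, two on-schedule readings are possible:

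| Missed | Last injection | Next, 8-week grid from last injection | Next, 8 weeks after missed visit |
|---|---|---|---|
| Week 20 | Week 8 | Week 24: 24 − 8 = 16 weeks | Week 28: 28 − 8 = 20 weeks |
| Week 32 | Week 20 | Week 36: 36 − 20 = 16 weeks | Week 40: 40 − 20 = 20 weeks |

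With ±7 days at both ends the range is 14 to 22 weeks. No reading gives 8 or 12. A patient seen to be active at an attended Week 20 or 32 is injected there, 12 weeks after the last dose.

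**The case against.** **The scoring follows the definition.** A reassigned patient really is on q8w until study exit, so is not on exclusive q12w. The rule is prespecified and the endpoint is secondary and descriptive. This stands, and is why the planned analysis should be kept. It does not answer the question of durability on retinal findings, which needs a second version. Nor is the rule uniformly conservative, because Week 44 is left out.

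**Missed visits will be visible.** SAP 2.4.1 tabulates missed treatments and visits by visit, and 2.6.1.6 tabulates disease activity by visit. True, but neither table links an absence to an individual patient's switch.

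**Week 44 may be left out for good reason.** It is the last possible injection, so a reassignment there changes no study dose. That may explain the dosing rule; it does not settle how the analysis should score the patient.

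**A reader might infer that the dosing rules flatly contradict each other and give presumed-active patients the longest gap.** The documents do not support this. The next dose date after a miss is unstated, not expressly contradicted. The absence itself causes the gap. Without the rule, a patient who missed Week 20 would next be due at Week 32, which is 24 weeks after Week 8, and one who missed Week 32 at Week 44, also 24 weeks. On these readings the rule shortens the gap. A late injection could shorten it further, but the SAP lists out-of-window injections as deviations, and the unscheduled-visit text is written for patients who return early, so applying it to an overdue dose is an inference.

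**A reader might also infer that COVID-19 absences are scored through the deviation code.** In SAP Table 5-1 a COVID-19 missed visit leads to no exclusion. That governs membership of analysis sets, not q12w status.

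**Conclusion.** The point holds for the two secondary q12w outputs and should be addressed. As written, a switch made only because Week 20 or 32 was missed is scored identically to observed activity, while a patient who misses Week 44 and completes on q12w is counted as maintained. The estimates therefore partly measure attendance.

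The size is unknown. The illustrative fall of about 2, 5 or 10 points rests on an assumed 55%, assumed miss rates of 2% to 10% per visit, and independence of absence from retinal status; the offset from Week 44 is not quantified. It would go too far to say that the q12w result is mainly a measure of attendance during the pandemic, since no attendance figure is given.

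Two limits apply. A patient already on q8w who misses Week 32 does not change either output. A patient who misses a visit and leaves before any q8w interval starts would appear to be censored in the Kaplan-Meier, while the treatment of that patient in the proportion is not specified.

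On dosing, the finding is a gap in the text: no passage gives the next visit and injection after a missed-visit reassignment, and each on-schedule reading gives 16 or 20 weeks against stated intervals of 8 or 12.

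**What to change.** **SAP 2.6.1.5 and 2.6.1.5.1**
1. Flag every q8w switch caused only by the missed-visit rule.
2. Keep the planned analysis, with these switches counted as loss of q12w.
3. Add a sensitivity version. In the Kaplan-Meier, censor flagged patients at their last attended disease-activity assessment. For the proportion, which cannot itself be censored, report either the Kaplan-Meier estimate or the Clopper-Pearson proportion among patients with the assessments observed. The Kaplan-Meier estimate is the safer choice: requiring all assessments drops maintained patients more readily than patients who switched early.
4. Handle a missed Week 44 consistently with Weeks 20 and 32 in both versions. This is a scoring convention for analysis, not a treatment rule.
5. State that the sensitivity version assumes missed visits are non-informative, and say how patients who leave after a missed visit enter the proportion.

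**Protocol.** The sponsor must reconcile Sections 6.5, 6.7.2 and 8 (including Unscheduled visits), so that they say when a patient reassigned after a missed visit is next seen and dosed. No dosing rule is proposed here.

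**Cost.** One flag from visit records already held, a short SAP change, a second version of two outputs, and a protocol clarification. No new data are needed.
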